#### Lesions that split in two

If a TL splits in two, then the LDs of the split lesions are summed and reported as the LD for the lesion that split.

#### Lesions that merge

If two TLs merge, then the LD of the merged lesion are recorded for one of the TL sizes and the other TL size is recorded as 0mm.

#### Change in method of assessment of TLs

CT, MRI and clinical examination are the only methods of assessment that can be used within a trial, with CT and MRI being the preferred methods and clinical examination only

used in special cases. If a change in method of assessment occurs, between CT and MRI this is considered acceptable and no adjustment within the programming is needed.

If a change in method involves clinical examination (e.g. CT changes to clinical examination or vice versa), any affected lesions are treated as missing.

#### Non-target lesions (NTLs) and new lesions – site investigator data.

At each visit, the investigator is to record an overall assessment of the NTL response. This section provides the definitions of the criteria used to determine and record overall response for NTL at the investigational site at each visit.

NTL response is derived based on the investigator's overall assessment of NTLs as follows:

Visit Responses	Description
Complete response (CR)	Disappearance of all NTLs present at baseline with all lymph nodes non-pathological in size (<10 mm short axis).
Progressive disease (PD)	Unequivocal progression of existing NTLs. Unequivocal progression may be due to an important progression in one lesion only or in several lesions. In all cases, the progression MUST be clinically significant for the physician to consider changing (or stopping) therapy.
Non-CR/Non-PD	Persistence of one or more NTLs with no evidence of progression.
Not evaluable (NE)	Only relevant when one or some of the NTLs were not assessed and, in the investigator's opinion, they are not able to provide an evaluable overall NTL assessment at this visit.
	Note: For subjects without TLs at baseline, this is relevant if any of the NTLs were not assessed at this visit and the progression criteria have not been met.
Not Applicable (NA)	Only relevant if there are no NTLs at baseline.

#### Table 3NTL Visit Responses

To achieve 'unequivocal progression' on the basis of NTLs, there must be an overall level of substantial worsening in non-target disease such that, even in the presence of SD or PR in TLs, the overall tumour burden has increased sufficiently to merit a determination of disease progression. A modest 'increase' in the size of one or more NTLs is usually not sufficient to qualify for unequivocal progression status.

Details of any new lesions are also recorded with the date of assessment. The presence of one or more new lesions is assessed as progression.

A lesion identified at a follow up assessment in an anatomical location that was not scanned at baseline is considered a new lesion and indicates disease progression.

The finding of a new lesion should be unequivocal: i.e. not attributable to differences in scanning technique, change in imaging modality or findings thought to represent something other than tumour.

New lesions are identified via a Yes/No tick box. The absence and presence of new lesions at each visit are listed alongside the TL and NTL visit responses.

A new lesion indicates progression so the overall visit response is PD irrespective of the TL and NTL response.

If the question 'Any new lesions since baseline' has not been answered with Yes or No and the new lesion details are blank, this is not evidence that no new lesions are present, but should not overtly affect the derivation.

Symptomatic progression is not a descriptor for progression of NTLs: it is a reason for stopping study therapy and is not included in any assessment of NTLs.

Subjects with 'symptomatic progression' requiring discontinuation of treatment without objective evidence of disease progression at that time should continue to undergo tumour assessments where possible until objective disease progression is observed.

#### Overall visit response - site investigator data

Table 4 defines how the previously defined TL and NTL visit responses are combined with new lesion information to give an overall visit response. Confirmation of progression is not required.

Table 4	Overall visit responses		
TARGET	NON-TARGET	NEW LESIONS	OVERALL VISIT RESPONSE
CR	CR or NA	No (or NE)	CR
CR	Non-CR/Non-PD or NE	No (or NE)	PR
PR	Non-PD or NE or NA	No (or NE)	PR
SD	Non-PD or NE or NA	No (or NE)	SD
PD	Any	Any	PD

TARGET	NON-TARGET	NEW LESIONS	OVERALL VISIT RESPONSE
Any	PD	Any	PD
Any	Any	Yes	PD
NE	Non-PD or NE or NA	No (or NE)	NE
NA	CR	No (or NE)	CR
NA	Non-CR/Non-PD	No (or NE)	Non-CR/Non-PD
NA	NE	No (or NE)	NE
NA	NA	No (or NE)	NED

## 4 STATISTICAL ANALYSIS

This section provides information on definition, derivation and analysis/data presentation per domain.

## 4.1 Analysis Sets

The analysis sets for this study are described in Table 5.

## **Table 5 Analysis Sets**

Analysis set	Description	Endpoint/Output
Enrolled analysis set	All subjects who sign the informed consent form (ICF).	Disposition
Safety analysis set	All subjects receiving at least 1 dose of study treatment. Subjects are summarised according to the actual treatment received.	Exposure Safety ORR BOR TTR DoR EORTC IL PGI-TT PK concentration listings Percentage Change in Target Lesion Tumour size Best Percentage Change in Target Lesion Tumour size
BICR Modified safety analysis set	All subjects receiving at least 1 dose of study treatment who have measurable disease at baseline	ORR (interim) BOR (interim) DCR (interim)

Analysis set	Description	Endpoint/Output
	by BICR and who have first dose at least 9 weeks prior to data cut off.	
Investigator Modified safety analysis set	All subjects receiving at least 1 dose of study treatment who have measurable disease at baseline by Investigator and who have first dose at least 9 weeks prior to data cut off.	ORR (interim) BOR (interim) DCR (interim)
Full analysis set	All subjects who are randomised in the study. The FAS is used for all the efficacy analyses including PROs. Treatment arms are summarized on the basis of randomised study treatment, regardless of the treatment actually received. Subjects who were randomised but did not subsequently receive study treatment are included in the analysis in the treatment arm to which they were randomised.	Baseline and demography ORR (for comparative analysis) PFS OS PROs
Pharmacokinetics (PK) analysis set	All dosed subjects with reportable ceralasertib or durvalumab plasma concentrations. Subjects are summarised according to the treatment received.*	PK concentrations
Pharmacodynamic analysis set	All subjects who receive at least 1 dose of study treatment with at least 1 reportable post-baseline pharmacodynamic measurement. Subjects are summarised according to the treatment received.*	Pharmacodynamic endpoints
BICR Response evaluable set	All dosed subjects who have measurable disease at baseline by BICR	ORR (sensitivity analysis)
Investigator Response evaluable set	All dosed subjects who have measurable disease at baseline by Investigator	ORR (sensitivity analysis)
BICR Interim response evaluable	All dosed subjects who have measurable disease at baseline by BICR assessment and who have first dose at least 17 weeks prior to data cut off.	ORR (interim) BOR (interim) DCR (interim)
Investigator Interim response evaluable	All dosed subjects who have measurable disease at baseline by Investogator and who have first dose at least 17 weeks prior to data cut off.	ORR (interim) BOR (interim) DCR (interim)

ORR: Objective Response Rate, DCR: Disease Control Rate, TTR: Time to Response, DoR: Duration of Response, PFS: Progression Free Survival, OS: Overall Survival, BOR: Best Objective Response; BIRC: Blinded Independent Central Review

TTR and DoR are reported for the subset of subjects with confirmed objective response.

\*Individual PK concentration data for any subjects who are excluded from the descriptive summary tables and/or figures are included in the listings and are flagged with an appropriate footnote.

Subject's data are flagged as being unevaluable in case no signed ICF is available. Subjects who are not randomised due to violation of one or more protocol defined inclusion or exclusion criteria are handled as screening failures.

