#### **3.2.2** Study Treatment

The main study is a Phase 2, randomised, open-label, multicentre, international study assessing the efficacy and safety of ceralasertib and ceralasertib plus durvalumab in subjects with unresectable or advanced melanoma and primary or secondary resistance to programmed death-ligand 1 [PD-(L)1] inhibition. Approximately 150 subjects are randomised, at a 2:1 randomisation ratio (approximately 100 subjects in Arm 1 and approximately 50 subjects in Arm 2) to the following intervention groups:

- Arm 1: Ceralasertib 240 mg BD oral tablets, from Days 1 to 7 plus durvalumab 1500 mg Day 8, IV infusion, Q28D, until progressive disease, (confirmed RECIST 1.1-defined radiological progression), unacceptable toxicity, withdrawal of consent, or if a study treatment discontinuation criteria is met.
- 2. Arm 2: Ceralasertib 240 mg BD oral tablets, from Days 1 to 7, Q28D, until progressive disease, (confirmed RECIST 1.1-defined radiological progression), unacceptable toxicity, withdrawal of consent, or if a study treatment discontinuation criterion is met.

Crossover within the study is not be permitted. There is no defined maximum treatment duration for the treatment arms as the subjects receive study treatment until progressive disease (RECIST 1.1-defined radiological progression), unacceptable toxicity, withdrawal of consent, or if a study treatment discontinuation criterion is met.

Randomisation into the treatment arms is stratified by:

• Resistance to prior immune-oncology treatment (primary/early relapse in adjuvant setting vs secondary resistance).

• Baseline lactate dehydrogenase (LDH) expression (below and equal to the upper limit of normal vs above upper limit of normal).

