## 4.2.1.2 Presentation

Subject disposition including screen failures and reason for screen failure is summarised and listed based on all subjects screened by treatment arm and for all subjects combined as defined by the current relevant tables, figures, listings (TFL) standards. The number and percentage of subjects for the following are summarised if applicable:

- Subjects screened;
- Screen failures;
- Subjects randomised;
- Subjects randomised, did not receive study treatment
- Subjects started treatment
- Subjects who received ceralasertib and subjects who did not receive ceralasertib;
- Subjects who received durvalumab and subjects who did not receive durvalumab (for combination arm);
- Subjects ongoing study treatment at data cut-off;
- Subjects who discontinued treatment (including reason),
- Subjects ongoing study at data cut-off;
- Subjects who terminated study.

Summaries on disposition due to global/country situation due to a pandemic are added to the disposition table if applicable. The number and percentage of subjects for the following summaries are added on if applicable:

- Subjects who discontinued treatment due to global/country situation;
- Subjects who withdrew from study due to global/country situation.

The study disruptions due to the global/country situation is also summarised as a separate table.

The number and percentage of subjects with confirmed or suspected Coronavirus Disease 2019 (COVID-19) infection during the course of the study are presented separately, including details on COVID-19 related interruptions impacting on visits, and study drug administration. Discontinuation of study intervention and/or withdrawal from study due to COVID-19 are presented separately.

Listings of subjects affected by the COVID-19 pandemic are presented detailing any affect and impact on the study. Issues reported in the Clinical Trial Management System are considered for presentation in listings as well.

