#### 4.3.1.1 Definition

ORR is defined as the proportion of subjects who have a complete response (CR), or partial response (PR), as determined by BICR per RECIST 1.1, prior to any evidence of progression (as defined by RECIST 1.1), that is confirmed at least 4 weeks later. ORR based on BICR is defined as the percentage of subjects with at least two post-baseline BICR-assessed visit response of CR or PR, with the denominator defined as the number of subjects in the Safety analysis set. For the sensitivity analysis, the subset of subjects in the Response evaluable set is used. For the comparative analysis of ORR between treatment arms the FAS is used instead (see Section 4.3.1.6).

The ORR analysis by BICR will be repeated for investigator data.

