# 4.3.1.4 Primary Analysis of Primary Endpoint

Summaries are produced that present the number and percentage of subjects with a confirmed tumour response (CR/PR). The ORR is presented for each treatment arm non-comparatively with a two-sided 95% CI using the Clopper-Pearson (exact probability) method. Subjects that have missing overall response assessments at all visits are considered as non-responders, and are therefore counted in the denominator of ORR. The main analysis of ORR is based on the Safety analysis set.

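### Read literally, the Safety-set grouping rule counts a dosed Arm 1 subject who never receives durvalumab as monotherapy in the primary ORR

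*SAP*

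**What the plan says.** Table 5 of the main-study SAP defines the Safety analysis set as "All subjects receiving at least 1 dose of study treatment. Subjects are summarised according to the actual treatment received". It assigns ORR, BOR, TTR, DoR and both target-lesion size endpoints to that set, together with exposure and safety. Section 4.3.1.1 defines ORR "with the denominator defined as the number of subjects in the Safety analysis set", and Section 4.3.1.4 confirms: "The main analysis of ORR is based on the Safety analysis set".

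Section 3.2.2 gives the Arm 1 regimen as ceralasertib "from Days 1 to 7 plus durvalumab 1500 mg Day 8, IV infusion, Q28D". Arm 2 receives the same ceralasertib on the same days without durvalumab. Section 4.2.1.2 includes a disposition count of "Subjects who received durvalumab and subjects who did not receive durvalumab (for combination arm").

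The Full analysis set row of Table 5 states: "The FAS is used for all the efficacy analyses including PROs". That set is grouped by randomised treatment. The same row then lists ORR only for the comparative analysis.

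**The concern.** Durvalumab starts a week after ceralasertib, so an Arm 1 subject who dies, withdraws or stops treatment in that week has received exactly the Arm 2 regimen. Under a rule based on treatment actually received, that subject leaves the combination denominator and joins the monotherapy denominator. The move is triggered by something that happens after randomisation and is probably related to outcome.

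The endpoint affected is the primary one. Section 3.2.1 defines success by a minimum observed ORR in the combination arm, so the denominator of that arm matters. The trial is open-label. If arm membership is left to programming, the choice can be made after responses are known.

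The gap reaches further in two ways. The interim and response-evaluable sets in Table 5 carry no grouping rule at all, although the stopping rules in Section 5 count responses out of subjects per arm. The on-treatment and treatment-emergent windows (Sections 3.2.4 and 4.3.12.2.1) are 30 days for monotherapy and 90 days for the combination, so the same undefined classification decides which window a subject gets.

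**Working it through.** **Inputs from the SAP**
- Section 3.2.2: "Approximately 150 subjects are randomised, at a 2:1 randomisation ratio (approximately 100 subjects in Arm 1 and approximately 50 subjects in Arm 2"). Check: 150 × 2/3 = 100 and 150 × 1/3 = 50, which agrees.
- Section 4.3.1.4: ORR by arm with an exact two-sided 95% Clopper-Pearson interval. Subjects with no response assessment count as non-responders and stay in the denominator.
- The target ORR, the success threshold and the interval widths are redacted, so no planned figure can be reproduced.

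**Assumptions not in the SAP**
- 20 responders of 100 in the combination arm and 5 of 50 on monotherapy, with all randomised subjects dosed.
- k Arm 1 subjects receive ceralasertib only; k is varied from 1 to 10.
- The k subjects are non-responders, except in the last check.

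**Why non-response is likely.** Sections 4.3.1.1 and 4.3.1.2 require two response assessments at least 4 weeks apart, both before progression and before further anticancer treatment. Section 3.2.10 schedules scans every 8 weeks. A subject who dies or leaves the study before Day 8 cannot meet this. One who stops treatment but stays under assessment could.

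**Formulas.** By randomised arm: 20/100 and 5/50. Literal rule: 20/(100 − k) and 5/(50 + k).

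| k | Combination ORR (95% CI) | Monotherapy ORR (95% CI) | Gap, points |
|---|---|---|---|
| 0 | 20/100 = 20.0% (12.7–29.2) | 5/50 = 10.0% (3.3–21.8) | 10.0 |
| 1 | 20/99 = 20.2% (12.8–29.5) | 5/51 = 9.8% (3.3–21.4) | 10.4 |
| 3 | 20/97 = 20.6% (13.1–30.0) | 5/53 = 9.4% (3.1–20.7) | 11.2 |
| 5 | 20/95 = 21.1% (13.4–30.6) | 5/55 = 9.1% (3.0–20.0) | 12.0 |
| 10 | 20/90 = 22.2% (14.1–32.2) | 5/60 = 8.3% (2.8–18.4) | 13.9 |

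**Other assumed ORRs** (combination 10% to 30%, monotherapy 4% to 20%). For k = 1 to 5 the combination ORR moves by +0.1 to +1.6 points and the monotherapy ORR by −0.1 to −1.8 points. For k = 10 the moves are +1.1 to +3.3 and −0.7 to −3.3 points.

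**If a moved subject responded.** With k = 5 including one responder: (20 − 1)/95 = 20.0% and (5 + 1)/55 = 10.9%. The combination ORR is unchanged and the monotherapy ORR rises, so the direction depends on non-response.

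**The case against.** The strongest reply is that the SAP never orders the reclassification. Grouping by treatment received can be read as dealing with dispensing errors rather than early stopping. The disposition table keeps subjects without durvalumab under the combination arm, and ORR is presented for each treatment arm. This stands to the extent that the SAP has no explicit instruction to move anyone. It does not remove the problem: the disposition table sets no rule for the Safety set, and the only rule written for that set, taken at its word, puts these subjects with monotherapy.

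The size is also open to challenge. Only a week separates the two first doses, so few subjects may be affected, and documented progression in that week is unlikely with 8-weekly scans. A delayed durvalumab dose is still a dose received. For up to 5 subjects the shift is under 2 points per arm, well inside the exact interval. All of this stands.

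A reader might infer that the planned comparison between the arms is biased. The documents do not support that. The odds ratio in Section 4.3.1.6 uses the FAS by randomised arm, as do PFS and OS, and the Safety-set ORRs are presented non-comparatively. A reader might also infer that first-week adverse events of Arm 1 in general would be reported under monotherapy. Only the events of subjects who never received durvalumab could be.

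The FAS sentence can be called loose wording, since the endpoint sections name their own sets consistently. It still contradicts the Safety-set row of the same table.

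**Conclusion.** The point holds as a defect in how the primary analysis assigns subjects to arms. The literal rule lets a post-randomisation event move dosed Arm 1 subjects into the monotherapy denominator, and nothing in the SAP overrides it for ORR, BOR, DoR, TTR or target-lesion change. If those subjects are non-responders, the combination ORR is biased up and the monotherapy ORR down.

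It would go too far to say that the bias is certain or large. It rests on the literal reading, on non-response in the moved subjects, and on a number of subjects that the SAP does not give. In the illustration, one such subject changes each ORR by 0.2 points; ten change the combination ORR by 2.2 points and the monotherapy ORR by 1.7. Shifts of that size matter mainly if the result falls close to the redacted success threshold. The conflict in Table 5 over which set serves efficacy needs correcting on any reading.

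**What to change.** Make three changes to Table 5:

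1. State that for efficacy endpoints, dosed subjects in the Safety set are summarised by randomised arm, and that the same holds in the interim and response-evaluable sets.
2. Define treatment received for the safety summaries when only one component was given, and state which follow-up window then applies. How these subjects are grouped for safety is the sponsor's choice; it needs to be written down before the data are analysed.
3. Correct the FAS sentence so that it agrees with the assignment of ORR, BOR, TTR and DoR to the Safety set.

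The cost is a few sentences and one treatment-variable derivation, with no new data. The drawback for the sponsor is that the combination ORR may be slightly less favourable than under the literal rule.

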#### 4.1.1.1 Presentation

The analysis sets are summarised by treatment arm and for all subjects combined. (nonefficacy summaries). Any exclusions from analysis sets are listed.

## 4.2 Study Population

The domain study population covers subject disposition, analysis sets, protocol deviations, demographics, baseline characteristics, medical history, disease characteristics, prior and concomitant medication, and study drug compliance.

## 4.2.1 Subject Disposition and Completion Status

## 4.2.1.1 Definitions and Derivations

Subjects screened is defined as informed consent received.

A subject is considered to have completed the study if they have completed all phases of the study including the last visit or the last scheduled procedure. Details can be found in section 4.4 of the CSP.

## 4.2.1.2 Presentation

Subject disposition including screen failures and reason for screen failure is summarised and listed based on all subjects screened by treatment arm and for all subjects combined as defined by the current relevant tables, figures, listings (TFL) standards. The number and percentage of subjects for the following are summarised if applicable:

- Subjects screened;
- Screen failures;
- Subjects randomised;
- Subjects randomised, did not receive study treatment
- Subjects started treatment
- Subjects who received ceralasertib and subjects who did not receive ceralasertib;
- Subjects who received durvalumab and subjects who did not receive durvalumab (for combination arm);
- Subjects ongoing study treatment at data cut-off;
- Subjects who discontinued treatment (including reason),
- Subjects ongoing study at data cut-off;
- Subjects who terminated study.

Summaries on disposition due to global/country situation due to a pandemic are added to the disposition table if applicable. The number and percentage of subjects for the following summaries are added on if applicable:

- Subjects who discontinued treatment due to global/country situation;
- Subjects who withdrew from study due to global/country situation.

The study disruptions due to the global/country situation is also summarised as a separate table.

The number and percentage of subjects with confirmed or suspected Coronavirus Disease 2019 (COVID-19) infection during the course of the study are presented separately, including details on COVID-19 related interruptions impacting on visits, and study drug administration. Discontinuation of study intervention and/or withdrawal from study due to COVID-19 are presented separately.

Listings of subjects affected by the COVID-19 pandemic are presented detailing any affect and impact on the study. Issues reported in the Clinical Trial Management System are considered for presentation in listings as well.

